1.0 BACKGROUND

Uterine leiomyoma, or fibroids, are benign smooth muscle tumors that occur in 25% of premenopausal women and cause heavy bleeding, pelvic discomfort, urinary and bowel dysfunction, and adverse pregnancy outcomes. Hysterectomy and myomectomy are the mainstay treatments for fibroids. However, many women seek minimally invasive, uterine-preserving therapy to avoid overnight hospitalization and allow for a rapid return to their usual activities.

The Radiofrequency ablation device is a new FDA approved surgical procedure that aims to effectively treat fibroids with a minimally invasive outpatient procedure. Radiofrequency ablation uses radiofrequency energy to heat fibroid tissue and cause instantaneous cell death. The necrotic cells are then reabsorbed by the lymphatic system resulting in decreased fibroid size and improved symptoms. The Radiofrequency ablation device is placed within the fibroid under ultrasound guidance during a standard outpatient pelvic laparoscopy.

There is limited outcome data on Radiofrequency ablation.^{1,2} In the pivotal trial for FDA approval of 135 women, fibroid symptoms decreased by 52% and fibroid volume decreased an average of 40% within 3 months of treatment.³ These therapeutic effects were persistent through 12 months of follow-up with 56% decrease in symptoms and 45% decrease in fibroid volume from pre-procedure values. Sixty one percent of study participants were very satisfied with treatment and 80% reported they would definitely recommend the treatment to a friend. One study participant required re-intervention for persistent or recurrent fibroid symptoms following Radiofrequency ablation treatment. The Radiofrequency ablation procedure resulted in minimal blood loss (median 33cc) and an average return to normal activities of 9 days. Therefore, Radiofrequency ablation treatment may result in decreased pain, less blood loss, faster return to normal activities, and lower rates of re-operation compared with either abdominal *or* laparoscopic myomectomy.

2.0 STUDY RATIONALE

The Radiofrequency ablation procedure offers women a new approach to fibroid treatment that improves bothersome symptoms with the potential for significantly less morbidity compared with current fibroid surgery. The existing studies of Radiofrequency ablation are all uncontrolled trials that demonstrate subjective and objective improvement in fibroid-related symptoms. However, no trials have been conducted to examine the benefit of Radiofrequency ablation in comparison with other surgical fibroid treatments. Our ultimate goal is to conduct a multi-centered, randomized, noninferiority trial of Radiofrequency ablation versus myomectomy (laparoscopic or abdominal) among women with symptomatic fibroids. This trial will provide gold standard evidence to determine if Radiofrequency ablation results in similar symptom improvement as myomectomy but offers the advantages of less operative morbidity and lower rates of re-operation for recurrent fibroid symptoms.

To prepare for a future multi-centered comparative trial of Radiofrequency ablation, we will first conduct an uncontrolled pilot study (the ULTRA study). The pilot will allow us to assess the feasibility of recruiting and retaining study participants to this surgical trial, and establish effective communication and organizational tools among the five study sites. We will also complete essential preparatory work for a future randomized trial; we will create and test study forms, a manual of operations, and a study database that can be easily adapted for a

comparative trial. The ULTRA pilot study will lay the foundation for a successful future comparative study of Radiofrequency ablation.

The ULTRA study will also provide preliminary data on the efficacy of Radiofrequency ablation in a “post-market” setting. This is the first Radiofrequency ablation trial after FDA approval in November 2012. Previous studies have enrolled a highly symptomatic patient population with a minimum menstrual blood loss of 200cc (normal is <80cc) to adhere to the requirements for FDA approval. However, in clinical practice, surgical treatment is offered to women with more moderate fibroid symptoms and we will enroll these patients in the ULTRA study. We will use ULTRA outcome data to estimate effect sizes and standard deviations to calculate an appropriate sample size for a future randomized trial.

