3.0 STUDY OVERVIEW

The ULTRA study is a single-arm trial of 100 premenopausal women with symptomatic uterine fibroids who undergo treatment with the Radiofrequency ablation device. We will evaluate changes in fibroid-related symptoms from pre-treatment values to 3, 6, 12, 18, 24, 30, and 36 months after Radiofrequency ablation. We will also assess operative outcomes including procedure duration, complications, blood loss, post-operative pain, and return to usual activities. We will determine long-term efficacy of Radiofrequency ablation by evaluating the rate of re-treatment for symptomatic fibroids after the Radiofrequency ablation procedure.

Study participants will be recruited at 5 sites within the UC Fibroid Network: UC Davis, UC Irvine, UC Los Angeles, UC San Diego, and UC San Francisco. UC San Francisco will serve as the Coordinating Center for the trial with oversight of all scientific and administrative aspects of the study. All study data will be stored securely in a HIPAA compliant, secure database monitored by the UC San Francisco Coordinating Center. A data safety and monitoring board will oversee participant safety and protection.

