4.0 STUDY OBJECTIVES

The ULTRA study will collect essential preliminary data to guide and inform a future multi-centered, randomized trial of Radiofrequency ablation versus myomectomy. The 2 primary study goals are:

1. To create and implement study protocols, measurements and procedures that will serve as a template for future comparative trials of Radiofrequency ablation.

We will evaluate the efficiency and timeliness of study recruitment. We will create a database and study forms with fibroid specific questionnaires, develop communications and study operations for the coordinating center and each study site, and assess the demand and interest for Radiofrequency ablation among symptomatic women.

2. To collect preliminary data on the changes in fibroid-related symptoms from baseline to 3 years after the Radiofrequency ablation procedure among women with symptomatic fibroids.

We will assess fibroid-related symptoms prior to Radiofrequency ablation treatment and every 6 months for 3 years after surgery. We will evaluate changes in both bleeding and bulk symptoms using validated questionnaires.

Secondary study objectives are as follows:

1. To determine the rate of re-intervention for recurrent fibroid symptoms following the Radiofrequency ablation procedure.
Study participants will be queried every 6 months about recurrent fibroid symptoms and interventions including medical management, myomectomy, uterine artery embolization, MR Guided Focused Ultrasound, or hysterectomy.
2. To evaluate short-term operative morbidity among women undergoing the Radiofrequency ablation procedure.

We will evaluate operative and perioperative morbidity including procedure duration, blood loss, complications, as well as post-operative pain and time to return of usual activities.

3. To evaluate gynecologists' performance during the "learning curve" of introducing the Radiofrequency ablation procedure into practice.

Gynecologists will be asked to rate the difficulty of the Radiofrequency ablation procedure and their confidence with the procedure among the first 10 study participants.

4. To examine the rate of pregnancy and pregnancy outcomes among women who desire future fertility following the Radiofrequency ablation procedure.

We will query study participants at baseline regarding the desires for future fertility and every 6 months after the Radiofrequency ablation procedure. We will ask participants to report any pregnancies and the outcome of those pregnancies.

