6.1 Participant Recruitment

Study participants will be recruited through the clinical practices of ULTRA investigators and among the general community of women seeking fibroid treatment. Advertisements for the study will be posted on the fibroid centers' and/or department website and in key clinical areas within our women's health clinics. We will also post advertisements in local newspapers and community boards. Study investigators will identify patients with symptomatic fibroids who meet the inclusion and exclusion criteria and invite them to participate in ULTRA. Study investigators will explain the Radiofrequency ablation procedure as well as the study protocol. Potential study participants will be offered alternatives to Radiofrequency ablation treatment as clinically indicated and available including medical management for heavy bleeding, myomectomy, hysterectomy, uterine artery embolization, and MR Guided Focused Ultrasound.

[figure not shown]

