7.5 Use of Radiofrequency ablation Outside of The ULTRA Study

The procurement of Radiofrequency ablation to the UC Operating Rooms is through the UC policies and procedures for IRB approved clinical trials, not through the pathway for device use in general clinical practice. Therefore, there will be no use of Radiofrequency ablation at study sites outside of participants enrolled in ULTRA/ULTRA Registry. Study investigators will not use Radiofrequency ablation for patients undergoing procedures who are not enrolled in ULTRA/ULTRA Registry. Among study participants, investigators will only use Radiofrequency ablation according to the ULTRA protocol.

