10.0 DATA AND SAFETY AND MONITORING PLAN

The Data and Safety and Monitoring Board will be an independent committee with members who are not employed by the University of California. The committee will consist of two academic obstetrician/gynecologist with expertise in clinical studies of gynecologic interventions and the conduct of clinical trials, and a biostatistician with expertise in clinical trials and interim monitoring.

The DSMB will be charged with overseeing participant safety and monitoring the scientific validity of the trial. Prior to initiating the study, the DSMB will review and approve the study protocol. The DSMB will meet in-person or by conference call every 4 months for the first year of the study or until all study participants are recruited. The DSMB will then meet annually during the remaining 3 years of the study. All DSMB meetings will consist of a closed session

with the 3 members of the DSMB and an open session that includes the Principal Investigator, Study Statistician, Study Project Director and clinical site Principal Investigators.

The DSMB will review the following outcomes during each meeting:

1. Recruitment and retention data including compliance with enrollment criteria, screening to enrollment ratio, dropout rate and reason for dropouts
2. Demographic data of study participants
3. Intraoperative and Immediate Postoperative Outcomes listed in Section 8.1.B.
4. Adverse Events as described in Section 9.0

The DSMB will make recommendations for protocol changes or amendments to the Principal Investigator and Steering Committee. The Principal Investigator will provide a written response to the DSMB within 2 weeks of the DSMB report. Full details of the DSMB are described in the ULTRA DSMB Charter.

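### ULTRA's single-arm accrual cannot show whether women would accept randomization between ablation and myomectomy, and no described measure asks them

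*Combined protocol and SAP*

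**What the plan says.** Section 2.0 names the end goal as a "multi-centered, randomized, noninferiority trial of Radiofrequency ablation versus myomectomy (laparoscopic or abdominal) among women with symptomatic fibroids" and presents ULTRA as the uncontrolled pilot that comes first. It gives recruitment feasibility as one reason for the pilot: "The pilot will allow us to assess the feasibility of recruiting and retaining study participants to this surgical trial". Section 4.0, primary goal 1, adds "We will evaluate the efficiency and timeliness of study recruitment" and a plan to "assess the demand and interest for Radiofrequency ablation among symptomatic women". The same goal also covers the database, forms, communications and site operations.

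Section 3.0 gives the design: "The ULTRA study is a single-arm trial of 100 premenopausal women with symptomatic uterine fibroids who undergo treatment with the Radiofrequency ablation device". Section 7.5 restricts access: "there will be no use of Radiofrequency ablation at study sites outside of participants enrolled in ULTRA/ULTRA Registry". The Registry is named there but not described. Section 6.1 states that "Potential study participants will be offered alternatives to Radiofrequency ablation treatment as clinically indicated and available"; myomectomy is among the alternatives it lists. No recording of reasons for declining is described.

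Section 10.0 has the DSMB review "Recruitment and retention data including compliance with enrollment criteria, screening to enrollment ratio, dropout rate and reason for dropouts". Section 12.0 plans analyses of patient-reported outcomes, operative outcomes, treatment failure, resource use and pregnancy. It contains no analysis of recruitment or retention.

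**The concern.** A woman deciding about ULTRA chooses between planned ablation and the usual alternatives. A woman deciding about the later trial would choose whether to let chance assign her to ablation or myomectomy. The first decision says little about the second. Strong demand for ablation could even go with reluctance to risk assignment to myomectomy, particularly where ablation is not otherwise available at the sites.

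At stake is the recruitment part of the pilot's purpose. If the plan is followed exactly, the investigators will know how fast women join a study that plans ablation for all of them. They will not know what share would have joined a randomized one. Once enrollment closes, the women who were screened cannot be asked again under the same conditions.

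**Working it through.** **No plan figure applies.** The only calculated design figure is the 7.2-point detectable UFS-QOL change in Section 12.0. It reproduces (a two-sided paired t-test at 90% power with SD 21.7 needs 98 women for 7.2 points), but it has no bearing on recruitment. The documents give no accrual target, no feasibility threshold and no rate of willingness to be randomized.

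**Search for a measure.**
- Section 8.1 (outcomes): symptom questionnaires, perioperative outcomes, treatment failure, adverse events and pregnancy. Nothing on randomization.
- Section 8.2 (baseline): participant and gynecologist characteristics. Nothing on randomization.
- Section 6.2 (consent): the investigator asks which other treatment the woman would want if ablation proves impossible at surgery. This is close, but it is a different question.
- Section 10.0 (DSMB): enrollment ratio and dropout, with no item on randomization and no target.
- Section 12.0: no analysis of recruitment.

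**Direction.** A woman who would accept either allocation would, in general, also accept ablation. Among the same women at the same sites, those willing to be randomized are then a subset of those willing to join ULTRA, and ULTRA accrual is an upper bound. The exception is a woman who leans toward myomectomy and so declines ULTRA, but who would let chance decide. Such women would reduce the overstatement, which is why decliners need to be asked too.

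**Size, for illustration.** Let a be ULTRA accrual per month and w the share of enrollees who would accept randomization, with no willing decliners. Randomized accrual is a × w, so reading a as randomized accrual overstates it by a/(a × w) = 1/w. All values of w are assumed:

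| w (assumed) | 1/w |
|---|---|
| 0.2 | 5.0 |
| 0.4 | 2.5 |
| 0.5 | 2.0 |
| 0.6 | 1.7 |
| 0.8 | 1.25 |

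**What one question would yield.** With 100 respondents the 95% half-width is 1.96 × √(w(1 − w)/100):
- w = 0.5: 1.96 × 0.0500 = 9.8 points.
- w = 0.3 or 0.7: 1.96 × 0.0458 = 9.0 points.
- w = 0.2 or 0.8: 1.96 × 0.0400 = 7.8 points.

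Wilson intervals are 13% to 29% at 20%, 40% to 60% at 50%, and 71% to 87% at 80%. The 100 enrollees alone would supply this precision. The number of decliners who would answer is unknown.

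**The case against.** The strongest reply is that the plan never makes the projection being criticized. No section carries ULTRA's recruitment rate into the next protocol; what Section 2.0 commits to carry forward is estimates of effect and variability for a sample size. The surgical trial in its feasibility sentence can be read as ULTRA itself. The later trial is described only as multi-centered, so it might use other sites or reach women who declined ULTRA. This stands, and for that reason the claim is that overstatement is likely, not that it will occur.

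Three further replies also stand in part. Primary goal 1 is mostly about protocols, forms and operations, which do not depend on randomization. A reader might infer that the whole goal fails, and the documents do not support that. Section 10.0 already collects the screening-to-enrollment ratio, dropout and its reasons, so only their reporting in Section 12.0 would be new. And the study forms, the manual of operations and the recruitment figure were not available for this review, so the most that can be said is that the question is not listed among the described measures.

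None of this supplies a measure of acceptance of randomization. Even if the feasibility sentence refers only to ULTRA, Section 4.0 says the study's data are meant to inform the randomized trial.

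**Conclusion.** The point holds as a low-cost improvement. As described, ULTRA accrual cannot show acceptance of randomization. It is likely to overstate randomized accrual from the same women at the same sites, assuming few women who decline ULTRA would have agreed to be randomized. The size cannot be computed from the documents; 5-fold to 1.25-fold follows only from an assumed 20% to 80% willingness.

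Two stronger readings should be resisted. A reader might convert the gap into extra months of recruitment for the later trial. That would need an accrual period and a future sample size. The DSMB schedule in Section 10.0 refers to the first year or the end of recruitment, which is not an accrual target, and Section 2.0 leaves the future sample size to be worked out from ULTRA data. A reader might also infer that ULTRA is the only route to ablation at these sites. Section 7.5 names the Registry as well, and the documents do not say whether access would stay restricted during the later trial.

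**What to change.** - **Screening log:** add one item, put to eligible women who are approached, both enrollees and decliners willing to answer. Ask whether she would join if treatment were assigned by chance between ablation and myomectomy and, if not, why. The consent form is the wrong place, because decliners do not sign it.
- **Section 12.0:** report the proportion willing with a 95% confidence interval, separately for enrollees and decliners. Add enrollment per site-month and the screening-to-enrollment and retention data already prepared for the DSMB.
- **Sections 2.0 and 4.0:** state that accrual alone supports a conclusion only about single-arm recruitment and retention.

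The cost is one question and one descriptive table. Recording decliners' answers may need ethics-board approval. Stated willingness is hypothetical and may itself overstate acceptance, so the report should say so.

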3.0 STUDY OVERVIEW

The ULTRA study is a single-arm trial of 100 premenopausal women with symptomatic uterine fibroids who undergo treatment with the Radiofrequency ablation device. We will evaluate changes in fibroid-related symptoms from pre-treatment values to 3, 6, 12, 18, 24, 30, and 36 months after Radiofrequency ablation. We will also assess operative outcomes including procedure duration, complications, blood loss, post-operative pain, and return to usual activities. We will determine long-term efficacy of Radiofrequency ablation by evaluating the rate of re-treatment for symptomatic fibroids after the Radiofrequency ablation procedure.

Study participants will be recruited at 5 sites within the UC Fibroid Network: UC Davis, UC Irvine, UC Los Angeles, UC San Diego, and UC San Francisco. UC San Francisco will serve as the Coordinating Center for the trial with oversight of all scientific and administrative aspects of the study. All study data will be stored securely in a HIPAA compliant, secure database monitored by the UC San Francisco Coordinating Center. A data safety and monitoring board will oversee participant safety and protection.

4.0 STUDY OBJECTIVES

The ULTRA study will collect essential preliminary data to guide and inform a future multi-centered, randomized trial of Radiofrequency ablation versus myomectomy. The 2 primary study goals are:

1. To create and implement study protocols, measurements and procedures that will serve as a template for future comparative trials of Radiofrequency ablation.

We will evaluate the efficiency and timeliness of study recruitment. We will create a database and study forms with fibroid specific questionnaires, develop communications and study operations for the coordinating center and each study site, and assess the demand and interest for Radiofrequency ablation among symptomatic women.

2. To collect preliminary data on the changes in fibroid-related symptoms from baseline to 3 years after the Radiofrequency ablation procedure among women with symptomatic fibroids.

We will assess fibroid-related symptoms prior to Radiofrequency ablation treatment and every 6 months for 3 years after surgery. We will evaluate changes in both bleeding and bulk symptoms using validated questionnaires.

Secondary study objectives are as follows:

1. To determine the rate of re-intervention for recurrent fibroid symptoms following the Radiofrequency ablation procedure.
Study participants will be queried every 6 months about recurrent fibroid symptoms and interventions including medical management, myomectomy, uterine artery embolization, MR Guided Focused Ultrasound, or hysterectomy.
2. To evaluate short-term operative morbidity among women undergoing the Radiofrequency ablation procedure.

We will evaluate operative and perioperative morbidity including procedure duration, blood loss, complications, as well as post-operative pain and time to return of usual activities.

3. To evaluate gynecologists' performance during the "learning curve" of introducing the Radiofrequency ablation procedure into practice.

Gynecologists will be asked to rate the difficulty of the Radiofrequency ablation procedure and their confidence with the procedure among the first 10 study participants.

4. To examine the rate of pregnancy and pregnancy outcomes among women who desire future fertility following the Radiofrequency ablation procedure.

We will query study participants at baseline regarding the desires for future fertility and every 6 months after the Radiofrequency ablation procedure. We will ask participants to report any pregnancies and the outcome of those pregnancies.

6.0 STUDY POPULATION

We will recruit women with symptomatic fibroids who meet the following criteria:

INCLUSION CRITERIA

1. Premenopausal (at least 1 menstrual period in last 3 months)
2. Age >21years
3. Fibroids are associated with heavy bleeding, pelvic pressure or discomfort, urinary or bowel symptoms, or dyspareunia
4. Desires surgical management of fibroids
5. Uterus ≤16 weeks in size
6. All fibroids ≤ 10cm in maximum diameter by ultrasound or MRI assessment *within the last year*.
7. Total number of fibroids ≤6 by ultrasound or MRI assessment *within the last year*. (For this study "Fibroids" will be leiomyomas > 2cm)
8. Had a Pap smear within the last 3 years with appropriate follow-up and treatment for cellular abnormalities
9. Endometrial biopsy indicates no hyperplasia or cancer (biopsy only required if age >45 years and has anovulatory heavy bleeding)
10. Able to tolerate laparoscopic surgery
11. Able to give informed consent

EXCLUSION CRITERIA

1. Planned treatment for infertility
2. Pedunculated fibroid with thin stalk (total stalk length is <25% maximum diameter of fibroid)
3. Intracavitary (FIGO Type 0) fibroid
4. Symptomatic fibroids are *only* FIGO Type 1 (submucosal with ≥ 50% intracavitary)
5. Planned concomitant surgical procedure in addition to treatment of uterine fibroids
6. Use of Essure or any other metallic, implantable device within pelvis
7. Pregnancy
8. Pelvic infection with the last 3 months
9. History of pelvic malignancy and/or pelvic radiation
10. Known or high suspicion for dense pelvic adhesions
11. Fibroids treated by myomectomy, uterine artery embolism, radio-frequency ablation, MRI Guided focused ultrasound, or cryomyolysis within the last 3 months

Inclusion of Women who Plan Future Pregnancy: The Radiofrequency ablation device has not been studied among women who desire future fertility. Therefore, the FDA states that Radiofrequency ablation is "not recommended for women planning future pregnancy". We will *include* women in ULTRA who desire future fertility because we aim to evaluate the impact of Radiofrequency ablation on pregnancy rates and pregnancy outcomes. Women who hope to become pregnant have limited treatment options. They are generally only offered myomectomy because of the 5% chance of ovarian failure following uterine artery embolization and the limited experience with pregnancy following MR Guided Focused Ultrasound. Radiofrequency ablation treatment may be a safe option for women who plan future fertility because the treatment is directed solely to the fibroid, not the surrounding myometrium. Potential study participants will

be informed of the Radiofrequency ablation FDA guidelines for women planning future pregnancy. Study investigators will emphasize the unknown outcomes of Radiofrequency ablation on future fertility and review the following potential risks:

- A decreased ability to become pregnant
- An increased risk of miscarriage
- An increased risk of pregnancy complications such as placenta abruption, that can injure the fetus, or in rare cases, result in fetal death
- An increased risk of uterine rupture during labor, resulting in injury to the patient or fetus, including the rare possibility of fetal death

